6.4.3 Participant Assessment of Procedural Pain

The participant will give an assessment of procedural pain on an 11-point scale ranging from 0 (no pain) to 10 (worst pain imaginable). The Pain Assessment Chart with an assigned numerical rating between 0 (smiling) and 10 (crying) will be used to assess pain at Day 0, as reference in Figure 4. The pain scale will be assessed immediately after each lesion treatment session.

Pain levels will be grouped into four categories: No Pain (Score of 0), Mild Pain (Scores of 1-3), Moderate Pain (Scores of 4-6) and Moderate-to-Severe Pain (Scores of 7-10). The number and percentage will be tabulated for each category of pain, averaged for overall pain and may be analyzed against other parameters.

Figure 4: Pain Assessment Chart

6.5 Sample Size Determination

No formal hypothesis tests will be performed for this study, so the sample size was selected to produce a representative sample of BCC lesions to determine whether treatment effects are consistent across study participants. A maximum of 30 participants will be treated to allow for assessment of the endpoints outlined in this protocol.

6.6 Populations for Analyses

The following populations are defined in Table 5.

Table 5. Population Descriptions for Analysis

Population	Description
Modified Intent-to-treat / Safety Population	All enrolled participants who began treatment with the CellFX system, irrespective of completed study treatment session, subsequent withdrawal, or deviation from the protocol.
Complete Treatment	This population consists of mITT participants who completed the entire CellFX treatment session.
Per-Protocol	Participants who received treatment, completed the CellFX treatment session, excision surgery and all required study visits.

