3.0 PROTOCOL

3.1 Study Objectives

The primary objectives of this study are to evaluate the safety and effectiveness of the CellFX System in adults with low-risk basal cell carcinoma. Table 1 below reflects the study endpoints associated with the two objectives.

Table 1. Study Objectives and Endpoints

Objectives	Endpoints
Safety To evaluate the safety of the CellFX System in adults with low-risk basal cell carcinoma	Primary: 
 • No serious adverse events related to CellFX Treatment or Procedure Secondary: 
 • Local Skin Reactions (Investigator) • Procedural pain assessment (Subject)
Effectiveness To evaluate the effectiveness of the CellFX System in adults with low-risk basal cell carcinoma	Primary: 
 • Complete histological clearance of the target lesion on microscopic evaluation of hematoxylin and eosin stains Secondary: 
 • Visible/clinical clearance of the target lesion by clinical/dermatoscopic evaluation • Partial response of the study lesion as assessed by WHO criteria ($\geq 50\%$ decrease in the product of the longest perpendicular diameters of each target lesion) • SCAR-Q Appearance Scale (Subject) • Manchester Scar Scale (Investigator) • Healing assessment questions (Investigator)

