3.2 Study Design

This study is designed as a prospective, multicenter IDE feasibility study in up to 30 adult participants with low-risk basal cell carcinoma utilizing the CellFX System at up to 6 sites within the United States. The study will consist of a single treatment session with the CellFX System followed by surgical tumor excision (with 5 mm margins) 60 days post-treatment.

Eligible subjects with 1-2 histologically confirmed, primary BCC lesion(s) who meet the inclusion and exclusion criteria will be enrolled. The BCC lesion(s) may be present anywhere on the body except neck, axilla, hands, feet, or genitals. In cases where the subject has more than 1-2 BCC lesions that meet the study criteria, the PI will select the lesion(s) to include in the study.

The subject will receive treatment of their confirmed BCC lesion(s) with the CellFX system. The treatment area will be evaluated at 3-days, 7-days, 14-days, 30-days and 60-days post-NPS treatment. At the 60-day follow-up visit, participants will undergo complete surgical excision of the tumor plus 5 mm margins. The subject will return for 3 more follow-up visits post-excision at 14 days (suture removal), 30 days and 60 days (typical skin check post-surgical excision) for a total of 9 study visits. The 3-day, 7-day, and 30-day post-NPS treatment follow-up visits as well as the 30-day post-surgical excision visit may be performed as telemedicine visits.

The excised tissue at the 60-day post-treatment visit will be shipped for histological analysis. Preparation and analysis of the excised tissue will be performed by Pinkus Dermatopathology Laboratory and a board certified dermatopathologist who has extensive experience in interpreting cutaneous neoplasms. Details of the preparation, shipment and analysis of the excised tissue are provided in the Tissue Handling and Analysis Procedure.

Photography of the study lesion(s) will be captured along with the investigator's assessments at all in-office visits. Detailed instructions for photography of the lesion area are provided in the photography instruction manual.

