3.6 Clinical Study Duration

It is anticipated that the enrollment of subjects in this study will take approximately 2-3 months in duration. All subjects included in this IDE feasibility study will return for follow-up visits at 3-days, 7-days, 14-days, 30-days, and 60-days post-NPS treatment. At the 60-day follow-up visit, participants will undergo complete surgical excision of the tumor plus 5 mm margins. The subject will return for 3 more follow-up visits at 14-days, 30-days, and 60-days post-excision for a total of 9 study visits. The total study duration will be 7 months.

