4.15 Discontinuation of CellFX Treatment Session

A participant may be discontinued from treatment with the CellFX System prior to completion of the entire treatment session in the event of intolerable pain or system failure of the CellFX System. If the study subject elects not to complete the treatment session, a study exit form shall be completed and documented as early termination. System failure of the CellFX System or component failure shall be documented on the Device Malfunction Form.

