6.2 Analysis of the Primary Effectiveness Endpoint

The count and proportion with the primary endpoint of histological clearance will be calculated along with a 95% confidence interval (CI). The primary population for this analysis will be the Per-Protocol population, though estimates will be produced for the modified intent-to-treat/ safety population (patients who begin treatment) and Complete Treatment population (subjects who complete all required cycles of treatment).

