6.3 Analysis of Secondary Endpoints

No formal hypothesis testing is planned for secondary endpoints. Any p-values comparing groups should be considered descriptive. The secondary endpoints will be evaluated using the modified intent-to-treat/ safety population, but these analyses may be repeated for complete treatment and per-protocol populations as well.

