6.9 Missing Data

All possible efforts will be made to minimize missing data in this study. However, based on previous studies, any missing data that does occur is likely due to missed follow-up visits. However, the sensitivity of the final results to missing data will be examined by comparing the primary outcomes to the results using a longitudinal model with the 60-day post treatment results, and a tipping-point analysis will be performed for the endpoints at 60 days to determine whether the missing data could change the inference compared to the primary models.

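### The primary clearance estimate drops subjects who have a valid Day 60 specimen if they miss a visit that yields no histology, including three visits after the outcome

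*Combined protocol and SAP*

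**What the plan says.** - **Endpoint.** Table 1 (section 3.1) gives the primary effectiveness endpoint as "Complete histological clearance of the target lesion on microscopic evaluation of hematoxylin and eosin stains".
- **Timing.** Section 3.2: "The excised tissue at the 60-day post-treatment visit will be shipped for histological analysis". This is Visit 6 in Table 3, and no other visit yields histology.
- **Analysis set.** Section 6.2: "The primary population for this analysis will be the Per-Protocol population". It adds estimates for the mITT/safety and Complete Treatment populations.
- **Definition.** Table 5 (section 6.6) defines Per-Protocol as "Participants who received treatment, completed the CellFX treatment session, excision surgery and all required study visits". The other two populations carry no visit condition.
- **Visits after the specimen.** Section 3.6: "The subject will return for 3 more follow-up visits at 14-days, 30-days, and 60-days post-excision for a total of 9 study visits".
- **Missing data.** Section 6.9: "based on previous studies, any missing data that does occur is likely due to missed follow-up visits". No rate is given.
- **Secondary endpoints.** Section 6.3: "The secondary endpoints will be evaluated using the modified intent-to-treat/ safety population".

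**The concern.** A subject's clearance status is settled once the Visit 6 tissue has been read. Attendance at Visits 2 to 5 adds nothing to that reading, and attendance at Visits 7 to 9 comes after it. Table 5 nevertheless makes all of these visits a condition for entering the primary analysis, and neither 6.2 nor 6.6 exempts a subject who has an evaluable specimen.

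Two things follow. Observed primary outcomes are lost from a study of at most 30 subjects, which widens the interval. Selecting on behaviour after the outcome also opens a route to selection bias whose direction cannot be known in advance. Section 1.6 says the data will be used to design a pivotal study, so the clearance rate and its interval are what the next trial would be planned on.

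The visit condition does not serve the Visit 9 scar and healing endpoints either, because 6.3 evaluates secondary endpoints in mITT.

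**Working it through.** **Plan's own figure.** There is none to reproduce. Section 6.5 sets a maximum of 30 participants without a power or precision calculation, and 6.2 asks for a 95% interval without naming the method. Exact (Clopper-Pearson) intervals are used here, with one lesion per subject.

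**Inputs from the documents.** Nine visits (3.2, 3.6, Table 3). Visit 1 is treatment and Visit 6 is excision. The non-excision follow-up visits are 2 to 5 (Days 3, 7, 14 and 30) and 7 to 9, seven in all. Visit 6 is left out of the count because missing it loses the specimen in any population.

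**Which visits count as required.** The word is not defined for this purpose. Visits 2, 3, 5 and 8 may be by telemedicine, but they are still scheduled visits. Table 3 codes Visits 7 and 9 as mandatory in-office visits, so at least two post-outcome visits count even on a narrow reading.

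**Assumptions.** Miss rate per visit q of 2% or 5%. All 30 subjects have a specimen.

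**Step 1, expected loss.** With independent misses over k visits, loss = 1 − (1 − q)^k. For example, k = 3 and q = 0.05 give 1 − 0.95³ = 14.3%. For misses that cluster within subjects, a beta-binomial model with intraclass correlation 0.3 is used. Then a + b = 0.7/0.3 = 2.333, b = (1 − q) × 2.333, and the probability of no miss is the product of (b + i)/(a + b + i) for i = 0 to k − 1.

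| Visits counted | Model | q = 2%: loss (left of 30) | q = 5%: loss (left of 30) |
|---|---|---|---|
| 7 and 9 (k = 2) | independent | 4.0% (28.8) | 9.8% (27.1) |
| 7 to 9 (k = 3) | independent | 5.9% (28.2) | 14.3% (25.7) |
| 7 to 9 (k = 3) | clustered | 4.4% (28.7) | 10.8% (26.8) |
| 2 to 5 and 7 to 9 (k = 7) | independent | 13.2% (26.0) | 30.2% (21.0) |
| 2 to 5 and 7 to 9 (k = 7) | clustered | 7.1% (27.9) | 16.9% (24.9) |

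**Step 2, precision.** If every lesion clears, the exact 95% lower limit is 0.025^(1/n): 88.4% for 30/30, 87.7% for 28/28, 86.8% for 26/26 and 83.9% for 21/21.

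**Step 3, direction.** Suppose the true result is 24/30 = 80.0% (95% CI 61.4% to 92.3%) and three subjects with specimens are dropped for missed visits.

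| Clear among the three dropped | Per-Protocol result | 95% CI |
|---|---|---|
| 3 | 21/27 = 77.8% | 57.7% to 91.4% |
| 2 | 22/27 = 81.5% | 61.9% to 93.7% |
| 0 | 24/27 = 88.9% | 70.8% to 97.6% |

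If attendance is unrelated to clearance, the number of not-clear subjects among the three dropped is hypergeometric (3 drawn from 30, of whom 6 are not clear). The first two rows then have probability 49.9% + 40.8% = 90.6%, and the last row 0.5%.

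**The case against.** The strongest reply is that no specimen goes unreported. Section 6.2 already commits to Complete Treatment and mITT estimates without a visit condition. Complete Treatment restricted to subjects with a specimen is in substance the set proposed here, so the change largely decides which estimate is called primary. The study has no formal test and no success threshold, so error rates are untouched. Section 9.10 has exclusions settled before database lock and listed by subject, which makes them visible.

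The likely size is also open to challenge. Four of the seven visits may be by telemedicine, 4.16 requires sites to try to reschedule missed visits, and 5.3 sets higher payments for Visits 7 to 9 plus all-visit bonuses. Section 6.9 names missed visits as the likely source of missing data but gives no frequency, and Visit 6 is itself a follow-up visit. The 30.2% loss is therefore the upper end of what was assumed, not a forecast. If attendance is unrelated to clearance, the shift in the rate is usually about two points or less.

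All of this stands as a limit on severity. It does not remove the defect. The primary estimate still leaves out observed outcomes because of attendance after the outcome. The tipping-point analysis in 6.9 deals with missing data, not with specimens that were read and then excluded by definition. Section 9.10 does not override Table 5.

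**Conclusion.** The concern holds. As written, the primary clearance estimate conditions on visits that carry no information about the endpoint, and three of those visits follow it. On the assumed miss rates, the post-outcome visits alone remove about 4% to 14% of subjects with histology, and all seven visits about 7% to 30%, depending on the rate and on clustering. The exact lower limit when all lesions clear falls by about 0.7 to 4.5 percentage points (88.4% to 87.7% at 28 subjects, to 83.9% at 21). The direction of any bias is unknown, and a material bias requires attendance to be linked to histology.

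This should be fixed. It is not fatal, because estimates without the visit condition are also planned and no test depends on the result.

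**What to change.** In Table 5, redefine Per-Protocol as participants who completed the CellFX session and have evaluable histology from the Visit 6 excision, and delete the condition on study visits. Tie the wording to Visit 6 with its Table 3 window (±5 days) rather than to Day 60 exactly, so that a new ambiguity is not introduced.

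Two related clarifications can go into the same amendment. First, mITT keeps treated subjects who have no specimen, but 6.2 does not say how they are scored. State a rule, for example a sensitivity analysis that counts them as not clear. Second, 4.15 says: "If the study subject elects not to complete the treatment session, a study exit form shall be completed and documented as early termination". State how that exit relates to continued data collection for mITT.

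The cost is one row of Table 5, one sentence in 6.2 and a clarification in 4.15, with no new data. The one consequence is that subjects who missed non-endpoint visits enter the primary set, so the headline rate may move slightly in either direction.

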6.7 Sub-Group Analyses

Subgroup analyses will be performed for the following subgroups:

- Lesion Size Tertiles
- Fitzpatrick skin type

6.8 Interim Analyses

No interim analysis is planned for this study.

6.9 Missing Data

All possible efforts will be made to minimize missing data in this study. However, based on previous studies, any missing data that does occur is likely due to missed follow-up visits. However, the sensitivity of the final results to missing data will be examined by comparing the primary outcomes to the results using a longitudinal model with the 60-day post treatment results, and a tipping-point analysis will be performed for the endpoints at 60 days to determine whether the missing data could change the inference compared to the primary models.

6.10 Exploratory Analysis

Exploratory analysis may be performed to compare the different BCC subtypes. Wound healing characteristics for the post-excision area will also be assessed and compared to the wound healing characteristics post-NPS.

Exploratory analysis may be performed for dermatologic similarities of skin type based on anatomic subcategories:

- Sun-exposed limbs
- Non-sun exposed limbs
- Torso

7.0 CLINICAL PHOTOGRAPHY

The Sponsor will use standardized photographic capture methods described in the photography instruction manual. Photographs will be taken at each in-office study visit. In order to ensure consistent serial clinical photography is achieved during the study, all subject photographs will be reviewed (monitored) on an ongoing basis. Digital images will be transferred/stored in a secure, password protected portal.

8.0 ADVERSE EVENTS

Pulse Biosciences will classify each reported Adverse Event according to ISO 14155:2011. All protocol specific AEs, whether device-related or not, will be recorded on the AE case report form and reported. Data to be collected will include the description of the AE, onset, and resolution dates (or whether the AE is ongoing), severity, management/treatment, outcome, and determination of the relationship to the device and/or procedure. All AEs related to the lesion site(s) should be reported and classified by the site Investigator and be followed by the Investigator to determine the relationship of the AE to the device or the study procedure.

All AE information will be collected from enrollment through the last study visit at 60 days following the surgical excision of the BCC lesion(s) (120 Days after the CellFX treatment session). All AEs will be followed until the event has resolved (in the case of permanent impairment, the event will be followed until it stabilizes, and the overall clinical outcome has been ascertained). Medical occurrences that begin before receiving a CellFX treatment but after obtaining informed consent will be recorded on the Medical History section of the CRF rather than the AE section.

When reporting AEs/SAEs, the Investigator should include the following information:

- Description of event
- Onset of event
- Duration of event (including resolution dates or whether the AE is ongoing)
- Severity
- Relationship to device or procedure
- Action taken
- Subject outcome

Severity describes the intensity of an event and will be assessed as:

- **Mild:** The AE does not interfere in a significant manner with the subject's normal functioning level.
- **Moderate:** The AE produces some impairment of function but not hazardous to health.
- **Severe:** The AE produces significant impairment of function or incapacities and/or it is a hazard to the subject.

Relationship to device or procedure will be assessed as:

- **Unlikely:** There is no indication that the AE was caused by the investigational or standard of care device.
- **Possibly:** It cannot be excluded that the AE was caused by the investigational or standard of care device.
- **Likely:** A causal relationship between the investigational or standard of care device and the AE is at least a reasonable possibility, i.e. there is evidence or argument suggesting a causal relationship.

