3.3 CellFX Procedure

The intended CellFX treatment device is described as the CellFX® System using the skin contacting component referred to as the “tip”. The three available tip sizes for this study are the 5.0mm x 5.0mm, 7.5mm x 7.5mm, and 10.0mm x 10.0mm tips defined in length and width, which may range from 2.0mm to 3.0mm in depth. When a treatment tip is attached, the CellFX Handpiece delivers a timed series of energy pulses, referred to as a “Cycle”. The subject will be treated with appropriate tip sizes according to the size of the BCC lesion. The tip depth will be selected according to the guidelines defined in **Table 2a** below. The BCC lesion(s) will be treated with a pre-determined treatment energy level per tip size within the range provided in **Table 2b**.

Table 2a: Treatment Tip Depth Selection Guidance

Tip Depth (mm)	Criteria
2.0	Standard recommended treatment depth tip
3.0	Lesions with BCC located in the deeper dermis in the diagnostic biopsy sample. Diagnosed nodular/non-superficial BCC lesion located on the back or shoulder where skin is thicker and where the 2mm depth tip may not be sufficient.

Table 2b: Treatment Level Range per Tip

Tip Size (L x W, mm)	Minimum Treatment Level per Cycle (mJ/mm ³)	Maximum Treatment Level per Cycle (mJ/mm ³)
5.0 x 5.0	45	155
7.5 x 7.5	40	85
10.0 x 10.0	20	85

For this device, the term treatment level (TL) refers to the energy density value (mJ/mm³) delivered to the tissue by the treatment tip per cycle. These treatment levels do not exceed the maximum safe ranges of settings previously tested in clinical studies. Multiple cycles of energy may be delivered with one or more tip sizes in order to treat the entire BCC lesion(s) along with a defined 5 mm margin during a single CellFX treatment session.

A tattoo will be applied prior to the CellFX treatment to identify the treatment area for evaluation. Four tattoo marks will be placed to identify the margin of the treatment zone within the tissue area of the eventual ellipse of the excision. The tattoo may be “touched up” or re-applied at future visits as needed. The tattoo will be applied to the area of the skin designated to be removed during the surgical excision of the BCC lesion on Day 60 (Visit 6). An analgesic will be used to manage potential treatment discomfort during the CellFX treatment.

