4.0 STUDY PROCEDURES

4.1 Screening

Recruitment will be conducted via direct communication by the investigator and/or his/her designated staff, advertisement and/or office ads. The Informed Consent discussion and signature process will be conducted by the investigator and/or designated staff. No study-specific assessments will be performed prior to obtaining consent.

A Screen Failure will be defined as a subject who did not meet one or more of the following criteria:

- Did not meet all inclusion and/or exclusion criteria
- Did not sign informed consent
- Signed the informed consent but did not subsequently undergo a treatment with the CellFX system

A screen failure will not be assigned a subject ID and information on this subject will not be entered in the electronic database. Information will be transcribed on the enrollment/screen failure log.

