4.5.2 Definition of Enrollment

Once the subject has been consented and has received a CellFX treatment, the subject will be considered enrolled and each enrolled subject will be assigned a unique Study Identification Number.

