4.5.3 CellFX Treatment Procedure

- 1-2 clinically diagnosed BCC lesion(s) that meet the study criteria will be selected by the treating investigator. The identified lesion(s) will be labeled.
- Baseline photographs will be taken (prior to use of analgesic for pain management and prior to tattooing).
- Baseline clinical measurements of the BCC lesion(s) shall be taken
- The site investigator will perform a baseline lesion(s) assessment.
- A template will be applied to the skin and used to map out the treatment application.
- A tattoo (4 marks) will be applied within the area designated for excision to mark the treatment zones for the purpose of identifying the treatment area during evaluation.
- An analgesic for pain management, such as local injection of lidocaine, will be administered to the selected study lesion area(s).
- Each study lesion will be treated with the CellFX system per Table 2 according to the treatment tips utilized.
- The total number of treatment cycles with the CellFX system will be recorded.
- The subject will be asked to rate his/her pain immediately after the treatment session for each lesion treated with the CellFX system by using a numerical rating score, depicted in Figure 4.
- Post-procedure lesion assessment will be performed by the investigator.
- Post-procedure photographic images of each selected lesion will be taken.
- A light bandage and/or any physician recommended dressing may be applied before the subject leaves.
- Any adverse events will be identified and documented.

4.6 3-Day Follow-up Visit (Visit 2)

- This visit may be performed in-office or as a telemedicine visit.
- Photographic images of each study lesion will be taken. Photographs are not required if the visit is not performed in-office.
- All lesions will be examined and clinically assessed by the site investigator. If the visit is not performed in-office, clinical assessment is not required.
- A light bandage and/or any physician recommended dressing may be applied post-evaluation.
- Any adverse events will be identified and documented. If the visit is not performed in office, the clinical site must inquire regarding any adverse events either by phone call, text, e-mail or video conference.

4.7 7-Day Follow-up Visit (Visit 3)

- This visit may be performed in-office or as a telemedicine visit.
- Photographic images of each study lesion will be taken. Photographs are not required if the visit is not performed in-office.

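### Read literally, the AE start rule in Section 8.0 and the screen-failure rule in 4.1 leave a serious reaction to the pre-treatment tattoo or analgesic out of a primary safety endpoint that covers the procedure

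*Combined protocol and SAP*

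**What the plan says.** - **Endpoint.** Table 1 (Section 3.1) states the primary safety endpoint as "No serious adverse events related to CellFX Treatment or Procedure". Section 6.4.1 restates it as the incidence of serious AEs or complications associated with applying NPS, procedure and treatment both included, reported as a count and proportion with a 95% CI.
- **AE window.** Section 8.0: "All AE information will be collected from enrollment through the last study visit". Section 4.5.2: "Once the subject has been consented and has received a CellFX treatment, the subject will be considered enrolled". Section 8.0 then deals with the interval before treatment: "Medical occurrences that begin before receiving a CellFX treatment but after obtaining informed consent will be recorded on the Medical History section of the CRF", as an alternative to the AE section. It makes no exception for serious or procedure-related events.
- **Untreated subjects.** Section 4.1 counts as a screen failure anyone who "Signed the informed consent but did not subsequently undergo a treatment with the CellFX system". It continues: "A screen failure will not be assigned a subject ID and information on this subject will not be entered in the electronic database". What remains is an entry on the enrollment/screen failure log.
- **Order of steps.** Section 3.3: "A tattoo will be applied prior to the CellFX treatment to identify the treatment area for evaluation". Section 4.5.3 (CellFX Treatment Procedure) lists the tattoo, then the analgesic (local lidocaine injection is given as an example), then CellFX.
- **Population.** Table 5 limits the safety population to enrolled participants who began CellFX.
- **Text pointing the other way.** Table 3 ticks adverse events at Visit 1, and 4.5.3 closes with an instruction to identify and document any AEs.

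**The concern.** The endpoint claims to describe the safety of the procedure as well as of the energy delivery. Two study interventions, the tattoo and the analgesic, fall between consent and the first cycle, which is the interval that Section 8.0 sends to Medical History. There are two cases.

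1. The reaction begins before the first cycle and the subject is still treated. The event stays on the CRF, but as medical history. The severity, relationship and outcome fields that Section 8.0 requires for an AE are not required there.
2. The reaction stops the session before any cycle. The subject becomes a screen failure and leaves the numerator, the denominator and the database.

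In both cases the departure favours the procedure. The sites also hold conflicting instructions: Section 8.0 says Medical History, while Table 3 and 4.5.3 say to record AEs at that visit. Section 1.6 says that the data will be used to design a pivotal study, and event details not recorded on the day may not be recoverable later.

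**Working it through.** **The chain of rules**

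| Step | Source | Consequence |
|---|---|---|
| AE collection begins at enrollment | 8.0 | Nothing earlier is in the AE window |
| Enrollment needs consent and a received CellFX treatment | 4.5.2 | The window opens with CellFX |
| Events after consent but before CellFX | 8.0 | Medical History |
| Tattoo and analgesic precede CellFX | 3.3, 4.5.3 | Reactions that begin before the first cycle are outside the window |
| Consented, not treated | 4.1 | No ID, no database record |
| Safety population | Table 5 | Untreated subjects excluded |

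Table 3 gives the tattoo its own row, apart from CellFX treatment, so the tattoo is clearly before treatment. The analgesic has no row, and its place rests on the order of the list in 4.5.3. Reactions that begin after the first cycle, or after a tattoo touch-up at a later visit, are inside the AE window and unaffected.

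**Size**

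The plan states no figure to reproduce: 30 is a maximum with no power calculation behind it (Section 6.5), and the CI method is not named. I assume the exact (Clopper-Pearson) interval.

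- For x = 0, the upper limit is 1 − 0.025^(1/n). With n = 30 this is 11.6%; with n = 29 it is 11.9%.
- For x = 1, the lower limit is 1 − 0.975^(1/n) and the upper limit is the 0.975 quantile of Beta(2, n − 1). With n = 30 this gives 0.1% to 17.2%; with n = 31, 0.1% to 16.7%.

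| One serious pre-cycle reaction | As written | If counted |
|---|---|---|
| Subject then treated, 30 in all | 0/30: 0% (0 to 11.6%) | 1/30: 3.3% (0.1 to 17.2%) |
| Subject not treated, 29 others treated | 0/29: 0% (0 to 11.9%) | 1/30: 3.3% (0.1 to 17.2%) |
| Subject not treated, 30 others treated | 0/30: 0% (0 to 11.6%) | 1/31: 3.2% (0.1 to 16.7%) |

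**How likely is one such event?**

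The documents give no rate. For an assumed rate p per subject, the chance of at least one in 30 is 1 − (1 − p)^30:

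| Assumed p | Chance of at least one in 30 |
|---|---|
| 0.5% | 14% |
| 1% | 26% |
| 2% | 45% |
| 5% | 79% |

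Section 1.5 reports about 700 subjects treated with NPS and no serious related adverse events. Taken as 0/700, the exact upper limit is 1 − 0.025^(1/700) = 0.53%, close to the lowest row. That reading is itself an assumption, because the AE windows and tattoo use in those studies are not described.

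**The case against.** The best case for the plan has several parts.

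- **Scope of the endpoint.** Section 6.4.1 speaks of the application of NPS, and procedure is not defined step by step. The relationship scale in 8.0 asks only about causation by a device. A tattoo or analgesic reaction is therefore not beyond doubt within the endpoint; including it rests on Table 1 and on the headings of 3.3 and 4.5.3. This stands, and it is why the fix must define the term.
- **Start of treatment.** CellFX treatment could be read as the whole session, which would bring the analgesic inside the AE window. That is possible for the analgesic. It is hard to sustain for the tattoo, given 3.3 and Table 3.
- **Visit 1 recording.** Table 3 and 4.5.3 call for AE recording that day. True, but Section 8.0 is the specific rule on where events in this interval go, so the result is a conflict and not a repair.
- **Legitimate purpose.** Screening and treatment may fall on different days (Section 4.5), so a Medical History rule for events unrelated to the procedure is reasonable. This stands; only its end point needs to move.
- **Rarity.** Lidocaine allergy is an exclusion criterion, the event must meet the SAE definition in 8.1.3, and it must begin in a short interval. The study is a feasibility study without inferential tests. This stands, and losing one untreated subject from the denominator moves the upper limit only from 11.6% to 11.9%.

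A reader might also infer three stronger things that the documents do not support. The first is that these events escape expedited reporting. The SAE row of Table 6 runs from when the site learns of the event and does not depend on enrollment or CRF section. The second is that 8.0 contradicts the AE definition in 8.1.1. That definition says what an AE is, whereas 8.0 says when AEs are collected. The third is that every subject receives an injected analgesic. Injection is only an example in 4.5.3.

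**Conclusion.** The concern holds as a defect in the wording of the AE start point and the screen-failure rule. Followed literally, those rules keep a serious reaction that begins at the tattoo or analgesic step out of the primary safety endpoint. If the subject is then not treated, the event also stays out of the database and the safety population, even where an expedited SAE report reaches the sponsor.

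The conclusion rests on two readings: that procedure in Table 1 includes the steps listed in 4.5.3, and that receiving CellFX means the delivery of cycles. Both are the more natural reading, but neither is stated outright.

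The effect is small in expectation and large if it occurs. One event would move the result from 0% to 3.3%, the upper limit from 11.6% to 17.2%, and the Table 1 endpoint from met to not met. At the rate compatible with the experience reported in Section 1.5 (at most about 0.5%, under the 0/700 assumption), the chance of seeing one in 30 subjects is at most about 15%: 1 − (1 − 0.0053)^30. The documents do not show that any event has been or will be lost.

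**What to change.** 1. **Section 8.0:** start AE recording at the first CellFX-procedure step, tattoo or analgesic, whichever comes first. Limit the Medical History rule to events that begin before that step. This also brings 8.0 into line with Table 3 and the closing step of 4.5.3.
2. **Sections 4.1 and 4.5.2:** assign an ID and a database record to any consented subject in whom such a step was started, even if no cycle was delivered.
3. **Section 6.4.1:** state that the tattoo and analgesic steps count as procedure. List serious procedure-related events in untreated subjects alongside the primary safety endpoint, separately from the treated safety population, so that the Table 5 denominator is unchanged.
4. **Section 8.1.1:** reconcile the sentence limiting sponsor reporting to dermatologic AEs with Table 6, which attaches that limit only to the residual AE category. Serious procedure-related events that are not dermatologic, such as a systemic reaction to an analgesic, should be captured. Without this, the first three changes could still miss them.

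The cost is protocol and CRF wording, slightly more data collection and probably at most a handful of extra subject records. The downside is that the safety figure may look less favourable.
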